6.2 Access to source documents and data handling

Access to patient information gathered throughout the course of this study will be strictly restricted to the members of the research team, specifically, the study investigators, research assistants involved in data collection and data entry, the statistician, and others in the event of a serious adverse event. Others who may gain access to the data would include the members of the Hospital Institutional Ethics Board who oversee the ethical conduct of the study; monitors assessing the accuracy of the data collection and entry; and Natural Health Product Directorate, Health Canada that oversees the use of Natural Health Products, including Traditional Chinese Medicine.

7.0 COMPENSATION

There will be no costs to patients for participating in this study. The study drug and research procedures will be provided to them free of charge.

Taxi vouchers will be provided to cover the cost of getting to and from the hospital for 3 out of 5 visits. The remaining 2 visits are considered standard of care.

If patient suffer an injury as a result of participating in the study, necessary medical treatment will be available at no additional cost. Unless required by law, compensation for such things as lost wages, disability or discomfort due to such an injury will not be offered.

Chinese Herbs protocol

Protocol title: A feasibility study of Chinese herbs to manage cancer-related symptoms in patients with advanced non-small-cell- lung cancer

NCT **02331394**

Date of the SAP **15-Nov-2015**

Statistical Analysis Plan

- Data will be analyzed using IBM SPSS statistics software (Version 20 for Windows).
- Simple descriptive statistics (percent, means with standard deviation; proportions) will be used to summarize the data.
- The Functional Assessment of Cancer Therapy-Lung (FACT-L) Quality of Life (QOL) questionnaire will be reported as:
 1. FACT -L total score
 2. The scores of the five individual subscales
 3. The composite Trial Outcome index (TOI), which is the sum of the functional and physical well-being and the lung cancer symptoms subscales.
- A Clinically Meaningful Change (CMC) in symptom scores is defined as a 6-point change in TOI.
- Two points difference will be used as a CMC for ESAS symptoms.
- Comparisons of repeated measures will be made using paired sample *t* test, which will compare subjects data at 2 different times: baseline and end of the study.
- A P value of 0.05 will be considered statistically significant.

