2. OBJECTIVES

2.1 Primary objectives:

- To assess the acceptability and feasibility of conducting a 6-week intervention with a standard CH formula designed to treat symptoms commonly experienced by patients with advanced NSCLC.

Acceptability will be assessed using the following questions at the end of the study:

- **Indirectly** from adherence and feasibility (see below)
- **Directly** from responses to the following questions:
 - i) “*Was the Chinese Herb treatment used in this study easy to take?*” Yes / No
 - ii) “*If you experienced any problems or side effects taking the Chinese Herb treatment used in this study, please tell us what these were.*” (Free text)
 - iii) “*If it was available, would you be willing to take the Chinese Herb treatment used in this study again?*” Yes / No / Don’t know

Feasibility will be assessed using the following indices:

- Willingness to participate: proportion of subjects enrolled from number of patients approached .
- Completion rates: proportion of enrolled subjects who completed study (including final assessment) (threshold for positive study: 60%)
- Adherence rates: Proportion of doses taken of number prescribed (threshold for positive study: 66%)

2.2 Secondary objectives:

- a) Assess the magnitude of the patients' quality of life response and symptoms change after the 6 -week intervention compared to baseline.
- b) Estimate an appropriate sample size for the fully implemented study

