4.4 Method of Treatment

After written informed consent has been obtained and eligibility has been established the patient will be asked to complete FACT-L and ESAS questionnaires. The patients will be offered the choice of taking the CH formula in capsules or sachets and given instructions about recommendations to improve palatability. The formula should be taken with meals 3 times a day (each dose is either 1 sachet or 4 capsules) for six-weeks. Patient will be instructed to complete a diary each day to confirm adherence to treatment and to indicate the reason(s) that any doses were missed or treatment was stopped. A two-week supply of the CH capsules/sachets will be dispensed to patient at the start of the study. Every two weeks thereafter diaries will be collected/checked with the patient and a new diary dispensed with the next two-week supply of formula. The written instructions about dosage, frequency, dosage timing and what to do in the event of an adverse reaction will be given to patients.

Study of Chinese herbs and lung cancer patients

Principal Investigator: [name]

Patients will be allowed to maintain their concomitant medications during the trial with exception of over-the-counter herbal supplements.

4.5 Withdrawal.

Patients may withdraw at any time during the trial for the following reasons:

1. Patient no longer wishes to participate
2. The patient's doctor makes the decision to withdraw the patient if any side effects are suspected.
3. An allergic response or adverse reaction to the Chinese herbs
4. A change in clinical status necessitating emergency admission for treatment
5. Evidence of worsening liver function or need to start medication included in the exclusion criteria.
6. Reduction of chemotherapy dose due to Grade 3 toxicity

In case if participation terminated prematurely, patient will still be asked to attend for the end of the study visit.

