5.4 Patient-Reported Outcomes

Symptoms and health status will be assessed using the Functional Assessment of Cancer Therapy-lung (FACT-L) and ESAS, (Edmonton Symptom Assessment System)(Appendix 3). The FACT-L is a 36-item self-report questionnaire that evaluates quality of life in lung cancer patients [77, 78]. Twenty-nine items measure physical, social, emotional and functional well-being; The final 7 items constitute the Lung Cancer Symptom Scale (LCSS)[79].

The questionnaires, available in French and English, will be distributed by the staff and completed by the patient. The questionnaire(s) will be completed on Day 1 (prior to any other discussions with study personnel) and at each visit (every 2 weeks) until study completion at 6 weeks. Study personnel will review all questionnaires for completeness before the patient leaves the investigational site, and the hard copy originals of the questionnaires will be kept in the patient's research record for data verification.

Table 3 Schedule of Assessments

Table 3 Schedule of Assessments

	Screening visit	Visit 1 (0)	Visit 2 (2 wks)	Visit 3 (4 wks)	Study end (6wks)
Written Consent	+				
Medical history (including other medical conditions, cancer type and stage and all medications)	+				
Update medical history and verify all medication		+	+	+	+
Blood test as per standard of care	+	+	+	+	+
INR test			+		+
Physical exam as per standard of care	+	+	+	+	+
Vital signs	+	+	+	+	+
Height	+	+			+
Weight	+	+	+	+	+
Karnofsky performance status	+	+	+	+	+
CT chest as per standard of practice					
Revised Edmonton Symptom Assessment System		+	+	+	+
FACT-L		+	+	+	+
Chinese herbs Dispensed		+	+	+	
Diary Returned/Dispensed		+	+	+	+
End of study acceptability questionnaire					+

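### The only test of quality-of-life and symptom change uses patients with both a baseline and an end score, so the 6-week change may look somewhat too favourable; an all-visits analysis and a week-6 window would be a cheap improvement

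*SAP*

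**What the plan says.** The SAP lists one inferential method for repeated measures: a paired t test, "which will compare subjects data at 2 different times: baseline and end of the study". Its descriptive statistics are general and do not name weeks 2 or 4.

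Protocol section 5.4 has the questionnaires completed on Day 1 and "at each visit (every 2 weeks) until study completion at 6 weeks". Table 3 accordingly shows ESAS and FACT-L at weeks 0, 2, 4 and 6. It gives the end visit a nominal time of 6 weeks without a window.

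Section 4.5 (Withdrawal) includes these reasons: "A change in clinical status necessitating emergency admission for treatment"; the doctor "makes the decision to withdraw the patient if any side effects are suspected"; and "Reduction of chemotherapy dose due to Grade 3 toxicity". It adds that after premature termination the "patient will still be asked to attend for the end of the study visit". Section 5.4 also has staff check each form for completeness before the patient leaves.

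Section 2.1 counts a patient as completing only if the final assessment was done, and sets 60% as the threshold for a positive study. Section 3.2 plans 15 patients. Objective 2.2(a) is the size of the change from baseline after the 6 weeks. The SAP takes 6 TOI points as clinically meaningful.

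**The concern.** The contrast itself matches objective 2.2(a). The question is who is left in it. A paired test needs both scores, so a patient who lacks the end score drops out of the estimate, and any week 2 and 4 scores that patient gave enter no test.

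The loss may be selective. Emergency admission, suspected side effects and Grade 3 toxicity plausibly accompany worse scores. Other listed reasons, such as the patient's wish or the start of an excluded medication, need not. If sicker patients go missing, the completers' mean change is too favourable, and there is no control arm in which a similar bias could cancel.

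Two rules are also absent. Without a week-6 window, an end visit held early could be paired as if it were the 6-week value. And nothing says explicitly whether a week-6 score obtained after stopping treatment is used.

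At stake is the secondary estimate in 2.2(a), which section 8.0 hopes will give an early indication that the treatment works.

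**Working it through.** **Inputs from the documents.** 15 patients (section 3.2); completion threshold 60% (section 2.1); scores at weeks 0, 2, 4 and 6 (section 5.4); clinically meaningful TOI change 6 points (SAP). The plan gives no power, SD or dropout figure for this test, so there is no stated result to reproduce.

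**How many can be missing.** 15 × 0.60 = 9 completers, so a positive study allows up to 15 − 9 = 6 without a final assessment. This is a floor for success, not a forecast.

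**Size of the bias in general.** With completion rate c, bias = (1 − c) × (completers' mean change − non-completers' mean change). If non-completers do 6 points worse, this is 0.4 × 6 = 2.4 at 60% and 0.2 × 6 = 1.2 at 80%. If they do 10 points worse, it is 0.4 × 10 = 4.0 at 60%.

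**Simulation. Every input in this paragraph is an assumption.** 15 patients, true change 0, TOI SD 12, 1,000 trials per setting (Monte Carlo SE of the paired bias 0.07 to 0.18). Correlation was AR(1) with 0.7 per visit, exchangeable 0.7, or mixed (0.5 + 0.5 × 0.5^lag). Dropout before weeks 2, 4 and 6 had log-odds rising by 0.05, 0.1 or 0.2 per TOI point lost since baseline at the last observed visit. Per 12-point loss these are odds ratios of exp(0.6) = 1.8, exp(1.2) = 3.3 and exp(2.4) = 11.

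| Setting | Bias of the paired change |
|---|---|
| All withdrawn patients attend at week 6 | 0 |
| 40% withdraw, half of them attend at week 6 | +0.3 to +1.5 |
| 80% complete, no withdrawn patient attends | +0.4 to +2.4 |
| 60% complete, no withdrawn patient attends | +0.6 to +4.1 |

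The last row, by dropout strength, is +1.4/+2.8/+4.1 (AR(1)), +0.6/+1.2/+2.0 (exchangeable) and +0.9/+1.6/+2.9 (mixed). Over the same settings an SD of 10 gives +0.5 to +3.0 and an SD of 15 gives +1.2 to +5.6.

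*Hand check of the second row.* With true change 0 and 60% completing, the non-completers' mean is −(0.6/0.4) = −1.5 times the completers' mean. If half of them attend, the observed mean is (0.6 − 0.2 × 1.5)/0.8 = 0.375 times the completers' mean. So 0.375 × 4.1 = 1.5 and 0.375 × 0.6 = 0.2, which agrees with the table within Monte Carlo error.

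**Random error for scale.** With 9 pairs the 95% CI half-width is t(8) × SD × √(2(1 − r))/√9, with t(8) = 2.306 and r the correlation between weeks 0 and 6. For SD 12:
- r = 0.343 (AR(1)): 10.6
- r = 0.5625 (mixed): 8.6
- r = 0.7 (exchangeable): 7.1

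**Does an all-visits model help?** In the 60% row, a REML mixed model with random intercept plus AR(1) was within 0.4 of zero in all nine cells. Its RMSE was lower in all nine (2.8 to 4.2 against 3.1 to 5.9), and its coverage was 95 to 98% against 87 to 95%. Those data fit the model's covariance, which flatters it. Two harder cases:
- Random-slope data that the model does not fit (SD rising from 12 to 17, or from 10 to 18): model +0.5 to +2.2, paired +1.7 to +5.7.
- Dropout driven by the current, unobserved change (60% completion): model +0.9 to +3.8, paired +1.5 to +6.3.

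**The case against.** A fair defence has four parts.

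- *The plan already limits the loss.* Withdrawn patients are asked to the end visit, forms are checked on site, and nothing in the SAP excludes a patient for stopping treatment. On a plain reading, a withdrawn patient who attends is in the test. This stands, and it is why the milder rows of the table matter most. But attendance is requested, not assured, and the form check helps only those who come.
- *The largest figures stack adverse assumptions.* A bias near 4 points needs completion at the floor, no withdrawn patient attending, and an 11-fold dropout odds per SD of loss. This stands.
- *The model is not a cure.* Near-zero bias depended on a correct covariance, and at n = 15 roughly 30 to 58% of fits lay at the edge of the covariance grid that was searched, a sign of weak identification. This stands. The model still had less bias than the paired test under misspecified covariance and under unobserved dropout.
- *A simple paired change suits a 15-patient pilot.* It does answer 2.2(a), and no success threshold rests on its P value. This limits the severity, but the model uses data already collected and keeps the paired test beside it.

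A reader might infer that the week 2 and 4 scores are thrown away. The documents do not support that: the general descriptive statistics may report them. They are absent only from the test.

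**Conclusion.** The point holds as a minor one. The single planned test leaves out anyone without an end score, uses no interim scores, and has no stated week-6 window. The resulting change may be too favourable by an amount that the documents cannot fix. Under the assumptions above it runs from zero (all withdrawn patients attend at week 6) through about 0.3 to 1.5 and 0.4 to 2.4 points, to about 0.6 to 4 in the most adverse of the four attendance and completion settings, against a 6-point meaningful change. It would be larger if dropout followed deterioration that was never recorded. Except in that case or with a larger SD, the bias is smaller than the 7 to 11 point half-width from 9 pairs.

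Two stronger inferences are not supported. One is that the study's main conclusion is compromised: completion, adherence, willingness to participate and the acceptability questions do not use this test. The other is that a gain of several points is to be expected from dropout alone: 60% is a threshold, and neither the dropout mechanism nor attendance after withdrawal is known.

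**What to change.** Add to the SAP:

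1. **Estimate.** Week-6 minus baseline change with 95% CI from a REML linear mixed model, week categorical, all visits of all enrolled patients with a baseline score. Pre-state one simple covariance structure, for example random intercept plus AR(1), and a named fallback if it does not converge. Random intercept alone left up to +1.5 in the simulation, so its use should be reported. Use small-sample degrees of freedom, for example the number of week-6 scores minus 1; normal quantiles gave 91 to 96% coverage. Report the paired t test beside it. Say that the model assumes missing at random and reduces bias without guaranteeing its removal.
2. **Timing.** State a week-6 window. Assign an end-of-study visit outside it to the nearest scheduled week, not to week 6. Include week-6 scores obtained after stopping treatment.
3. **Missing scores.** Report the number of missing week-6 scores and the reasons, with deaths shown separately. Add one shift: missing week-6 TOI taken as 6 points worse than predicted. This lowers the estimate by 6 × 6/15 = 2.4 with 9 of 15 observed and by 6 × 3/15 = 1.2 with 12 of 15.

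Cost: SAP wording and a little programming, with no extra visits. If every week-6 score is present, the model and paired estimates coincide. The downside is a missing-at-random assumption and a weakly identified covariance at n = 15. Items 2 and 3 are worth adopting even if the sponsor prefers not to fit the model; the shift could then be taken from the completers' mean change.

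### The SAP tests FACT-L and ESAS changes at P = 0.05 with no lead score or exploratory label, plans no confidence intervals, and does not say how P and the CMC are read together

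*SAP*

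**What the plan says.** The SAP reports FACT-L in three forms: "FACT -L total score", "The scores of the five individual subscales", and "The composite Trial Outcome index (TOI), which is the sum of the functional and physical well-being and the lung cancer symptoms subscales". It gives two thresholds for clinical meaning. The CMC in symptom scores is "defined as a 6-point change in TOI", and "Two points difference will be used as a CMC for ESAS symptoms".

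On testing, it says that "Comparisons of repeated measures will be made using paired sample" *t* tests of baseline against end of study, and that "A P value of 0.05 will be considered statistically significant". It names no lead score, makes no multiplicity provision and gives no exploratory label. It plans no confidence interval. It does not list the scores to be tested, and it does not say whether the CMC is a patient-level or a group-level criterion.

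Protocol section 2.2(a) makes this a secondary objective about the size of the quality of life response and "symptoms change after the 6 -week intervention compared to baseline". The primary objective (section 2.1) is acceptability and feasibility. Its thresholds for a positive study are 60% completion and 66% adherence.

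**The concern.** Many correlated scores, each tested at 0.05 in at most 15 patients, make a chance finding on one of them likely. The cohort has no control group to set such a finding against. Section 8.0 hopes that the symptom data may offer preliminary evidence of effectiveness ahead of further trials, and objective 2.2(b) uses the study to size the next one. A stray significant subscale or symptom could be carried forward as a signal.

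There is also a mismatch between question and tool. Objective 2.2(a) asks how large the change is, and a P value does not measure that. The SAP has a yardstick for size in its CMCs, but no interval to lay against it and no rule for a result where significance and the CMC point different ways.

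**Working it through.** The documents give no familywise error rate, power or sample-size derivation, so there is no plan figure to reproduce.

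**Inputs**
- FACT-L scores (SAP): 1 total + 5 subscales + 1 TOI = 7.
- ESAS symptoms: number not given. Assumed 9 or 10, so 16 or 17 scores in all.
- Level: 0.05 per test (SAP). Sidedness is not stated; two-sided assumed.
- Pairs: 15 enrolled (protocol section 3.2), or 0.60 × 15 = 9 at the completion threshold (section 2.1).
- Correlation between score changes: not given. Assumed equal, from 0 to 0.7.
- SD of the paired changes: not given, so step 3 reports switch points.

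**Step 1. Independent tests, for reference.** The chance of at least one P < 0.05 under no change is 1 − 0.95^k: 30.2% for k = 7, 56.0% for k = 16 and 58.2% for k = 17. The scores cannot all be independent, because the total and the TOI are sums of subscales.

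**Step 2. Simulation under no change.** There were 100,000 simulated trials per cell, with equal-variance subscales and with the total and TOI built as exact sums. Chance of at least one P < 0.05:

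| Correlation | Pairs | FACT-L only (7) | With 9 ESAS items (16) | With 10 ESAS items (17) |
|---|---|---|---|---|
| 0 | 9 | 26.6% | 53.4% | 55.8% |
| 0 | 15 | 25.9% | 53.4% | 55.7% |
| 0.3 | 9 | 23.1% | 46.2% | 48.2% |
| 0.3 | 15 | 22.5% | 45.4% | 47.1% |
| 0.5 | 9 | 20.1% | 37.7% | 39.4% |
| 0.5 | 15 | 19.4% | 36.7% | 38.0% |
| 0.7 | 9 | 16.1% | 27.6% | 28.9% |
| 0.7 | 15 | 15.5% | 26.4% | 27.5% |

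The number of pairs hardly matters; the assumed correlation does.

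**Step 3. P against the CMC, if the CMC is read on the mean.** The smallest mean change reaching P = 0.05 is t(0.975, n − 1) × SD / √n.
- n = 15: 2.145 / 3.873 = 0.554 SD.
- n = 9: 2.306 / 3 = 0.769 SD.

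Dividing the CMC by that factor gives the SD at which the two criteria change places:

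| Score (CMC) | n = 15 | n = 9 |
|---|---|---|
| TOI (6 points) | 6 / 0.554 = 10.8 | 6 / 0.769 = 7.8 |
| ESAS symptom (2 points) | 2 / 0.554 = 3.6 | 2 / 0.769 = 2.6 |

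Above the switch SD, a mean change equal to the CMC is non-significant. Below it, some mean changes smaller than the CMC are significant. For example, at n = 15 a TOI change SD of 8 makes 4.4 points significant, while an SD of 12 requires 6.6 points. For an ESAS symptom with SD 3, the smallest significant mean change is 1.7 points at n = 15 but 2.3 at n = 9, so the disagreement can run either way.

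**The case against.** The strongest reply is that this is a secondary objective in a 15-patient feasibility cohort. No quality of life test decides whether the study is positive, so one might infer too much by calling the P value the study's only decision rule. That reply stands: the 60% and 66% thresholds govern the primary conclusion, and the CMCs are stated criteria too.

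A reader might also infer that the SAP contradicts itself. It does not. Statistical significance and clinical meaning are different criteria, and small samples often separate them. Nor does the SAP say that a change at the CMC will be reported as negative if P exceeds 0.05. If the CMC is meant per patient, the comparison in step 3 does not apply at all. What remains is a gap: the SAP does not say which level is meant or how the two criteria are combined.

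A third inference would be that the plan carries one fixed false-positive rate. It does not, because the ESAS item count and the correlations are absent from the documents. The top of the range needs zero correlation among the subscales and ESAS items, which is implausible for overlapping symptoms in the same patients. That every score is tested is likewise a reading, since the FACT-L scores are listed for reporting and the t test is prescribed without restriction. If fewer tests were intended, the SAP needs to name them.

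Finally, an unadjusted 95% CI that excludes zero carries the same information as P < 0.05, so intervals alone do not prevent selective reading. This is why the exploratory label is needed as well.

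**Conclusion.** The concern holds as an omission in the secondary analysis, of minor to moderate weight. The excess false-positive risk is present under every assumption tried: about 15% to 27% for the seven FACT-L scores, and about 26% to 56% once an assumed 9 or 10 ESAS items are added, against a nominal 5% for one test. These figures rest on all listed scores being tested two-sided, equal correlation between 0 and 0.7, and 9 or 15 pairs. The upper end should not be quoted as the expected value.

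The possible disagreement between P and the CMC is conditional on a group-mean reading and on SDs that the documents do not give. The firm finding is that the plan has no interval estimate for an objective about magnitude and no rule for reading P and the CMC together.

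**What to change.** In the SAP, designate the TOI change as the single tested quality of life outcome, since it already has a CMC. Label all other FACT-L and ESAS comparisons exploratory, with no significance claim. Report every mean change with its 95% CI, and read the TOI and ESAS intervals against the stated 6-point and 2-point CMCs. State that the CMC is also applied per patient, and give the numbers improved and worsened by at least that amount.

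The choice of TOI is a proposal. Another single score could serve if named before the data are analysed, but it would need its own CMC unless it is an ESAS symptom.

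The cost is a few SAP sentences. No new data are needed, and the intervals come from the same paired analysis. The downside is that fewer results can be called significant.
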